9.4 STATISTICAL ANALYSES

9.4.1 GENERAL APPROACH

Descriptive statistics (frequency distribution and percentage for categorical variables; mean, SD, median, interquartile range, minimum, maximum for continuous variables) of patient demographics, clinical characteristics, and medical history.

9.4.2 ANALYSIS OF THE PRIMARY EFFICACY ENDPOINT(S)

Statistical Methods:

Primary Outcomes: Efficacy

For each Knee Society Score, (objective score and subjective score), analysis of covariance (ANCOVA) will be used to examine the association between that score and intervention group (X4 brace, standard of care). The corresponding pre-op score will be included as a covariate in the model. Discharge location (home, inpatient rehabilitation) will also be included in the model. If the interaction between intervention group and discharge location is significant, then pairwise comparisons of intervention group within each discharge location will be examined within the ANCOVA model. If the usual assumptions of the ANCOVA model are not met, either a suitable transformation, or an appropriate nonparametric method will be used.

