3 OBJECTIVES AND ENDPOINTS

OBJECTIVES	ENDPOINTS	JUSTIFICATION FOR ENDPOINTS
Primary		
 To determine if patient postoperative outcomes, measured by the Knee Society Score, are improved by using the X4 brace with the Motion Intelligence platform To monitor the study group for any device related adverse events 	 To compare the Knee Society Scores, both objective and subjective scores, done preoperatively and at 8 weeks postoperatively between the control and study groups To monitor the study group for any device related adverse events 	The Knee Society Score is a validated tool used for assessing outcome in total arthroplasty patients Patients will be followed to ensure there are no issues with the utilization of the X4 brace
Secondary		
 To determine if there is a reduction in the rehabilitation costs (inpatient or outpatient) by using the X4 brace with the Motion Intelligence platform 	 To compare the number of inpatient days in a rehabilitation center between the control and study groups To compare the number of outpatient visits to a physical therapy center between the control and study groups 	To evaluate if the X4 brace provides user- friendly, cost-effective, enhanced patient recovery following total knee arthroplasty
 To evaluate patients satisfaction with the X4 brace with the Motion Intelligence platform 	 To evaluate patient's satisfaction with the X4 brace with the Motion Intelligence platform via the "System Usability Scale" (SUS) questionnaire (study group only) 	
 To evaluate patients compliance and adherence using the X4 brace with the Motion Intelligence platform 	• To measure patient's compliance using the X4 brace with the Motion Intelligence platform by counting how many days they used the platform as prescribed within an 8 week period. A patient will be	

OBJECTIVES	ENDPOINTS	JUSTIFICATION FOR
		ENDPOINTS
	considered compliant if they use the platform once a day.	
	 To measure patient's adherence using the X4 brace with the Motion Intelligence platform. Adherence is defined as performing the entire exercise routine as prescribed once a day. 	
 To evaluate provider satisfaction using the X4 brace with the Motion Intelligence platform 	 To evaluate provider satisfaction with the X4 brace with the Motion Intelligence platform via the "System Usability Scale" (SUS) questionnaire (study group only) 	In order for this technology to become part a postoperative regime the platform should be both effective and user friendly for the provider

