4 STUDY DESIGN

4.1 OVERALL DESIGN

Hypotheses: The X4 brace with the Motion Intelligence platform will provide an enhanced, cost-effective postoperative recovery following total knee arthroplasty (TKA).

This is a prospective, randomized clinical trial to evaluate the use of the X4 knee brace with the Motion Intelligence platform in patients having unilateral TKA. This brace is a FDA approved, marketed product being used as per the manufacturer's (DJO) marketed indications. Patients will be randomized to one to 4 cohorts:

This study is designed to determine if using a "virtual rehabilitation" device leads to enhanced recovery following total knee arthroplasty by improving patient objective and subjective outcome measures. These outcomes will be collected using a validated tool called the Knee Society Score (KSS)

(Appendix A). The KSS is a standard of care tool collected for all TKA patients pre-operatively and postoperatively at the 8 week visit.

- Cohort 1- Study group-Home discharge. Patients randomized to this group will be provided with the X4 brace and trained on the use of Motion Intelligence platform.
- Cohort 2- Control group-Home discharge. Patients randomized to this group will serve as the control group. There will be no changes to the standard of care recovery for a TKA patient.
- Cohort 3- Study group-Inpatient rehabilitation. Patients randomized to this group will be provided with the X4 brace and trained on the use of Motion Intelligence platform.
- Cohort 4- Control group-Inpatient rehabilitation. Patients randomized to this group will serve as the control group. There will be no changes to the standard of care recovery for a TKA patient.

No interim analysis is planned for this study. Randomization schedule will be done by the statistician via RedCap.

The DJO X4 brace will be provided to the patient at no cost. Study visits, hospitalization, inpatient and outpatient rehabilitation costs are standard of care and will be the responsibility of the patient. There will be no payment for participation in this study.

All study patients will complete a daily "Daily Patient Log" (Appendix B) starting the day after discharge from the hospital until postoperative day (POD) 56. This log will document the patient's location:

- o Rehabilitation center or
- Home physical therapy or
- Physical therapy center
- Hospital (re-admission)
- Return to work (if applicable)

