9 STATISTICAL CONSIDERATIONS

9.1 STATISTICAL HYPOTHESES

• Primary Efficacy Endpoint(s):

Knee Society Scores will be obtained prior to surgery, and at 8 weeks postoperatively

- Objective knee score (completed by the surgeon)
- Subjective knee score (completed by patient)
- Secondary Efficacy Endpoint(s):

All outcomes will be measured at 8 week postoperative visit or the visit closest to this time point

Outcomes for all patients regardless of discharge location

• Number of outpatient visits to a physical therapy center

Outcomes for patients discharged to inpatient rehabilitation

o Number of inpatient days in a rehabilitation center

Outcomes for patients randomized to the X4 brace with the Motion Intelligence platform

- Patient satisfaction with the X4 brace with the Motion Intelligence platform: Patients will complete the System Usability Scale (SUS)
- Compliance in using the X4 brace with the Motion Intelligence platform: Patients will be instructed to use the X4 brace twice a day. For each day, a subject will be considered compliant if they access the platform at least once a day, and non-compliant if they do not access at all the platform that day.
- Adherence using the X4 brace with the Motion Intelligence platform: For each day, a subject will be considered adherent if they perform the entire exercise routine as prescribed at least once a day, and non-adherent if they do not perform the entire exercise routine that day.
- Primary Safety Endpoint(s)
- Adverse Events related to the X4 brace will be collected in patients regardless of discharge location.

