9.2 SAMPLE SIZE DETERMINATION

Sample Size Justification:

Based on preliminary data (from the Total Knee Arthroplasty Registry), there were 244 patients treated under the standard of care, with a KSS subjective score obtained between 6 and 10 weeks after surgery. We will use this information to estimate the KSS subjective score for the standard of care group at 8 weeks after surgery. The mean KSS subjective score in these patients was 108.5, with a standard deviation of 27.5. We believe that a 10 point improvement is clinically meaningful. We further assume that the scores for those discharged to home, and those discharged to inpatient rehabilitation will be similar, (i.e. no interaction between intervention group and discharge location). Therefore, we will use a two sided two-sample t-test to simplify the calculation. In addition, the KSS subjective scores in our preliminary data were normally distributed, and so the calculation uses the raw (untransformed) data.

A sample size of 120 patients per group will yield 80% power to detect a 10 point difference between the two intervention groups using a two sided two-sample t-test at the 0.05 significance level. As

dropout is expected to be very low, no adjustment for attrition will be made. Therefore, the total sample size will be 240 patients (120 per group).

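### Two primary Knee Society Scores are tested separately with no rule for success, order or alpha; if either alone could carry the claim, the false-positive chance is about 7–10%

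*Combined protocol and SAP*

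**What the plan says.** The primary efficacy endpoint in section 3 is "To compare the Knee Society Scores, both objective and subjective scores, done preoperatively and at 8 weeks postoperatively", compared between the control and study groups. Section 9.1 lists the two scores side by side under the primary efficacy heading, the objective one completed by the surgeon and the subjective one by the patient.

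Section 9.4.2 sets the analysis: "For each Knee Society Score, (objective score and subjective score), analysis of covariance (ANCOVA) will be used". On adjustment it says: "The corresponding pre-op score will be included as a covariate in the model". Discharge location is also in the model. It then adds a conditional step: "If the interaction between intervention group and discharge location is significant, then pairwise comparisons of intervention group within each discharge location will be examined". No significance level is given for the treatment tests, the interaction or the within-location comparisons.

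The only level stated for a treatment comparison on KSS is the two-sided 0.05 in section 9.2, which concerns the subjective score alone. It takes a mean of 108.5, an SD of 27.5 and a 10-point difference, assumes no interaction with location, and says "we will use a two sided two-sample t-test to simplify the calculation". It concludes: "A sample size of 120 patients per group will yield 80% power to detect a 10 point difference". It does not call the subjective score the lead endpoint, and it gives no effect size or SD for the objective score.

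**The concern.** With two primary scores and no decision rule, the plan does not define what a positive trial is. Suppose one score is significant and the other is not. The same data then support a positive or a negative conclusion, depending on a rule chosen after the results are known. Section 10.1.2 lists attainment of the primary endpoint, in the singular, among possible grounds for termination, but that event is not defined.

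Two things follow. First, if success on either score is enough and each is tested at 0.05, the chance of a false claim exceeds the level stated in section 9.2. Second, a claim could rest on the objective score alone, for which no power was calculated. That score is completed by the surgeon, and section 6.3 says that investigators cannot be blinded.

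A secondary point is that section 9.4.2 opens within-location comparisons after a significant interaction without stating their role, while section 9.4.7 marks sub-group analyses as not applicable.

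**Working it through.** **Inputs from the documents.** Two primary scores (3, 9.1); a separate ANCOVA for each (9.4.2); two-sided 0.05, 120 per group, difference 10, SD 27.5 (9.2).

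**Assumptions.** The documents do not give the correlation ρ between the two test statistics (range 0 to 0.9 shown) or the correlation r between pre-op and 8-week scores (0 to 0.5 shown).

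**1. The plan's own figure.** The standardised difference is d = 10/27.5 = 0.364, and the noncentrality is d·√(120/2) = 2.82. The two-sided t-test at 0.05 has power 80.1% with 120 per group, and 120 is the smallest sufficient number. Section 9.2 reproduces.

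**2. Either overall test can carry the claim, no true effect on either score.** P(at least one) = 1 − P(|Z₁| ≤ 1.96 and |Z₂| ≤ 1.96), with Z₁, Z₂ bivariate normal and correlation ρ. At ρ = 0 this is 1 − 0.95² = 9.75%. In favour of the brace it is 1 − P(Z₁ ≤ 1.96 and Z₂ ≤ 1.96), which at ρ = 0 is 1 − 0.975² = 4.94%.

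| ρ | At least one false positive, either direction (nominal 5%) | In favour of the brace (nominal 2.5%) |
|---|---|---|
| 0 | 9.75% | 4.94% |
| 0.5 | 9.07% | 4.54% |
| 0.9 | 7.04% | 3.52% |

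The two-sided figure drops below 7% only above about ρ = 0.9 (6.5% at 0.95).

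**3. Both must succeed.** A false claim needs a rejection on a score with no effect, so its chance cannot exceed 5%. No adjustment is needed.

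**4. Subjective first, then objective.** If the subjective score has no effect, any claim needs a false rejection at the first test, so the chance is at most 5%. If it truly improves by 10 points and the objective score has no effect, a false claim needs both tests to reject. At ρ = 0 that chance is the power of the first test times 0.05. ANCOVA power uses d/√(1 − r²):

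| r | Power, subjective test at 0.05 | False objective claim, ρ = 0 |
|---|---|---|
| 0 | 80.1% | 0.801 × 0.05 = 4.0% |
| 0.4 | 86.5% | 0.865 × 0.05 = 4.3% |
| 0.5 | 90.0% | 0.900 × 0.05 = 4.5% |

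The last column falls as ρ rises; at r = 0 it is 3.4% at ρ = 0.5 and 2.5% at ρ = 0.9.

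**5. Equal split, 0.025 each.** The two-sided error for the pair is 1 − 0.975² = 4.9% at ρ = 0 and 3.6% at ρ = 0.9. Subjective power is 71% by the t-test of 9.2, 79% at r = 0.4 and 84% at r = 0.5.

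**6. Power to confirm the objective score as well.** This cannot be computed from the documents. For illustration only, take r = 0 and ρ from 0 to 0.7. If the objective standardised effect equals the subjective one, both are significant with probability 64% (0.801² at ρ = 0) to 71%. If it is 0.25 SD, whose single-test power is 48.8%, the probability is 39% (0.801 × 0.488 at ρ = 0) to 47%.

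**The case against.** The strongest reply is that the documents never say either score alone suffices. Section 4.1 describes a device that "leads to enhanced recovery following total knee arthroplasty by improving patient objective and subjective outcome measures", which can be read as requiring both, and under that reading there is no inflation. Section 9.4.2 treats each score in turn, but that describes how it is modelled, not what counts as success. The scores, model and covariates are all prespecified. This stands: the defect is an unstated rule, and the 7–10% is what one permitted reading would cost. It does not close the gap, because section 4.1 states a purpose and gives no decision rule.

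A second reply is that the aim is improvement, so a false finding against the brace would not be claimed as success. That also stands. The matching comparison is 3.5–4.9% against 2.5%, and it would be wrong to set those figures against 5%. The relative inflation is much the same.

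A reader might also infer that within-location comparisons add further chances of a false claim. If a gated single-location result could carry the claim, with the interaction tested at 0.05 and 41% of patients in inpatient rehabilitation, simulation gives about 11–15%. The documents do not support that reading. Section 9.4.2 says only that these comparisons will be examined, and both the interaction level and the location split are assumed.

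**Conclusion.** The point holds as a gap in the decision rule. Two primary scores are tested separately, with no both-or-either rule, no order and no alpha split, and the stated level and power belong to the subjective score only. If either overall test may carry the claim at two-sided 0.05, the chance of at least one false positive is about 7–10%, or 3.5–4.9% in favour of the brace against 2.5%. These figures rest on the assumed between-score correlation of 0.9 down to 0 and on the either-score reading. It would be too strong to say that the trial has a 7–10% error rate, because the plan does not commit to that reading; if both scores must succeed, there is no inflation. The undefined role of the within-location comparisons is secondary. The sample size in section 9.2 is correct for the test it describes.

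**What to change.** In sections 9.1 and 9.4.2, keep both scores primary and state an order:

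1. Test the overall treatment effect on 8-week subjective KSS at two-sided 0.05, by ANCOVA with pre-op score and discharge location.
2. Only if that is significant, test objective KSS at two-sided 0.05 with the same model.
3. State that the within-location comparisons triggered by the interaction are supportive and cannot carry the primary claim.

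The order follows the score on which the trial is sized. The sponsor may reasonably prefer to require both scores or to test each at 0.025; either controls the error of the overall tests, and item 3 would still be needed. The split lowers subjective power to 71% by the t-test of 9.2, or 79% at a pre/post correlation of 0.4. The power of the both-required rule depends on an objective-score effect that the sponsor would have to supply.

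The cost is an amendment with IRB approval before the data are analysed, with no extra patients. The downside of the ordered plan is that the objective score cannot carry the claim alone, and the chance of confirming it as well is unknown until an effect size and SD are given.

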5 STUDY POPULATION

5.1 INCLUSION CRITERIA

Inclusion Criteria:

- 1. Age > 18 or < 90
- 2. Able to read and speak in English
- 3. Patients having a unilateral total knee arthroplasty by Drs. [name] or [name]
- 4. Patients with a smart phone and internet able to access the Motion Intelligence Platform
- 5. Patient is freely able to provide consent
- 6. Patients willing to comply with the standard of care postoperative visit schedule (2 and 8 weeks)
- 7. Agree to complete the KSS 2013 version preoperatively and at the 8 week postoperative visit (standard of care)
- 8. Agree to complete the study required validated System Usability Scale at the 8 week postoperative visit (Appendix C)

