6.3 MEASURES TO MINIMIZE BIAS: RANDOMIZATION AND BLINDING

Randomization:

Prior to randomization, patients will be stratified according to discharge location (home, inpatient rehabilitation). Within each stratum, patients will be randomly assigned in a 1:1 ratio to the X4 brace with the Motion Intelligence platform or standard of care.

The Biostatistics Unit will develop a randomization procedure using a permuted block design within the REDCap system). Additional details of the procedure, including required record keeping, will be further developed upon approval of this protocol. The Biostatistics Unit has extensive experience in implementing and in producing detailed documentation for such procedures.

Blinding and Concealed Allocation

Due to the nature of the X4 brace, it is not possible to blind the investigators or the participants. The randomization assignment will be obtained from BRMS, after consent has been obtained, after it has been determined that the subject has met all inclusion/exclusion criteria, and after the discharge location has been determined.

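### The primary ANCOVA leaves out operating surgeon, a two-level factor fixed before randomisation; adding it would cost almost nothing and gain a little precision, probably not much

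*Combined protocol and SAP*

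**What the plan says.** Section 9.4.2 specifies a separate ANCOVA for the objective and the subjective Knee Society Score. Each model contains intervention group and the matching pre-operative score, and "Discharge location (home, inpatient rehabilitation) will also be included in the model". The interaction of group with discharge location is also examined. No other covariate is named.

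Section 6.3 stratifies randomisation by discharge location alone: "Within each stratum, patients will be randomly assigned in a 1:1 ratio". Surgeon is not a stratum. Sections 9.4.7 (subgroups) and 9.4.9 (exploratory analyses) are marked as not applicable, so surgeon does not enter there either.

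Three other places bear on the point:

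- Section 5.1 limits eligibility to "Patients having a unilateral total knee arthroplasty by Drs", followed by two (removed) names.
- Section 6.1.1 places randomisation after surgery, once discharge location is confirmed.
- Section 9.1 lists as a primary endpoint "Objective knee score (completed by the surgeon"; the subjective score is completed by the patient.

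The sample size in Section 9.2 rests on the subjective score only.

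**The concern.** The plan already uses covariate adjustment, yet omits a factor that has only two levels, must be known for every patient because eligibility depends on it, and is settled before allocation. It could matter in two ways. The surgeons' patients may recover differently, which could affect both scores. For the objective score, the two surgeons may also score differently.

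If either is so, two things follow. The part of the between-surgeon variation that the pre-operative score does not explain stays in the residual and widens the confidence interval. And because allocation is not balanced on surgeon, the arms may by chance differ in their surgeon mix, so that the estimate in this particular trial moves by the surgeon difference times the imbalance. What is at stake is precision and conditional balance, not validity.

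**Working it through.** **Inputs from Section 9.2.** "The mean KSS subjective score in these patients was 108.5, with a standard deviation of 27.5". "A sample size of 120 patients per group will yield 80% power to detect a 10 point difference between the two intervention groups"; the calculation is for a t test, two-sided at 5%. On attrition: "dropout is expected to be very low, no adjustment for attrition will be made".

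**Inputs not in the documents.** The between-surgeon difference D, one surgeon's share of cases p, and the SD of the objective score. I assume D of 0, 5 or 10 points on the subjective score and p = 0.5, with p = 0.7 as a check. I do not assume an SD for the objective score.

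**Step 1: reproduce the plan's figure.** The standard error of the difference is 27.5 × √(2/120) = 3.55. The two-sided noncentral t test with 238 degrees of freedom gives 80.1% power for 10 points, and 120 per group is the smallest number that reaches 80%. The normal approximation gives 119 per group, and 80.4% power at 120. The stated sample size is correct.

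**Step 2: precision from adjusting for surgeon.** A two-level factor with difference D and share p contributes variance p(1−p)D². Removing it leaves a residual SD of √(27.5² − p(1−p)D²). The test is repeated with one degree of freedom fewer (237).

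| D (points), p = 0.5 | Share of variance | Residual SD | SE | Power |
|---|---|---|---|---|
| 0 | 0% | 27.50 | 3.55 | 80.1% |
| 5 | 6.25/756.25 = 0.8% | √750 = 27.39 | 3.54 | 80.4% |
| 10 | 25/756.25 = 3.3% | √731.25 = 27.04 | 3.49 | 81.4% |

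With p = 0.7, power for D = 5 and D = 10 is 80.4% and 81.2%. If the surgeons do not differ, the lost degree of freedom has no visible effect on power.

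**Step 3: chance imbalance without adjustment.** The SD of the between-arm difference in one surgeon's share is √(2 × 0.25/120) = 0.0645. The 95% limit is 1.96 × 0.0645 = 0.1265, or about 12.7 percentage points in either direction. The estimate then moves by 0.1265 × D:

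- D = 0: no shift
- D = 5: 0.63 points, or 0.63/3.55 = 0.18 standard errors
- D = 10: 1.27 points, or 1.27/3.55 = 0.36 standard errors

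With p = 0.7 the limit is 11.6 percentage points and the shifts are 0.58 and 1.16 points. These are outer limits. An imbalance of one SD with D = 5 gives 0.0645 × 5 = 0.32 points.

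**Step 4: what the pre-operative score already does.** Steps 2 and 3 work from the raw SD, as the plan's own calculation does. If a surgeon effect is stable and present at both visits, the pre-operative covariate with slope β removes a fraction β of it and leaves (1−β)D. A difference that arises at or after surgery is not in the pre-operative score and is not removed that way. The figures above are therefore on the generous side for stable effects.

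**Step 5: objective score.** None of this carries over numerically, because 27.5 is the SD of the patient-completed score.

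**The case against.** The strongest reply is that this is a modelling preference. Randomisation is 1:1, so omitting a baseline variable leaves the estimate unbiased on average and the type I error controlled. Chance imbalance is already reflected in the standard error. The same argument could be made for age, sex or other baseline variables. No passage says that the surgeons differ in technique or scoring. Nor is there a power shortfall to repair: Section 9.2 used an unadjusted t test, so the pre-operative covariate alone should lift power above 80% (for an assumed correlation of 0.5, to about 90%).

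All of that stands, and it limits the point to an optional improvement. It does not remove the case for the term. Surgeon has only two levels, must be known for everyone, and cannot be affected by allocation, so a prespecified main effect cannot bias the comparison. Averaging over hypothetical repetitions does not help the one trial that draws an uneven surgeon mix.

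Three stronger readings are tempting and are not supported:

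- **A reader might infer that the primary analysis is biased or invalid.** It is neither.
- **A reader might infer a gain of several power points**, for instance by supposing that surgeon explains 5% or 10% of the variance (82.1% or 84.1% power). With a 50:50 split, those shares require surgeon differences of 2 × 27.5 × √0.05 = 12.3 and 2 × 27.5 × √0.10 = 17.4 points. Both exceed the 10 points that Section 9.2 treats as clinically meaningful, and nothing in the documents suggests differences that large.
- **A reader might infer that adjustment protects the surgeon-rated score against rater bias.** It does not. Section 6.3 says that investigators cannot be blinded, and a surgeon main effect does not remove scoring that differs by arm. Section 9.1 also refers only to the surgeon, without saying that this is the patient's own operating surgeon.

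**Conclusion.** The point holds as a low-priority improvement to a sound analysis. Operating surgeon appears in neither the stratification nor the primary model, and no other section brings it in.

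The benefit is probably small. On the subjective score, for assumed surgeon differences up to 10 points and an even split, power rises by at most about 1.3 percentage points (80.1% to 81.4%), and adjustment guards against a shift of at most about 1.3 points at the 95% limit of imbalance. Both figures rest on assumed differences and an assumed case split, and both shrink to the extent that the pre-operative score carries the surgeon effect. For the objective score, where the rating argument applies, the documents do not allow a figure. The sample size is correct and need not change.

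**What to change.** In Section 9.4.2, prespecify operating surgeon as a fixed two-level covariate in both primary ANCOVA models, alongside the pre-operative score and discharge location. It should be written in before outcome data are seen, since a later addition would be open to challenge.

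The cost is one model term and one of about 236 residual degrees of freedom, with no change to sample size, visits or procedures. The documents do not list surgeon among the captured variables, so the team should confirm that it is a database field; eligibility already requires it to be known. Unblinded rating of the objective score needs its own answer.
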